## 4.3.4 General Reporting Conventions

Continuous data will be summarized in terms of the mean, standard deviation (SD), median, minimum, maximum and number of observations (n), unless otherwise stated. The minimum and maximum will be reported to the same number of decimal places as the raw data recorded in the database. The mean and median will be reported to one more decimal place than the raw data recorded in the database. The standard deviation will be reported to two more decimal places than the raw data recorded in the database. In general, the maximum number of decimal places reported shall be four for any summary statistic.

Categorical data will be summarized in terms of the number of subjects providing data at the relevant time point (n), and percentages. Any planned collapsing of categories will be detailed in the SAP text and the data displays. Percentages will be presented to one decimal place. Percentages will not be presented for zero counts. Percentages will be calculated using the number of subjects in the analysis set (N) as the denominator.

Descriptive statistics for the 12-week study period will be presented by treatment group and visit, as applicable.

All statistical tests will be two-sided and will be conducted at the 5% significance level, unless otherwise specified.

P-values greater than or equal to 0.0001, in general, will be presented to four decimal places. P-values less than 0.0001 will be presented as "<0.0001".

## 4.3.5 Data Standards

The study data and analysis datasets will conform to the Clinical Data Interchange Standards Consortium (CDISC) standards including therapeutic area data standards for COPD. General standards include the Study Data Tabulation Model (SDTM) and Analysis Data Model (ADAM) and associated implementation guides.

#### 4.3.6 Software

All report outputs will be produced using SAS® version 9.4 for UNIX in a secure and validated environment in accordance with procedures.

## 4.4 Study Subjects

## 4.4.1 Disposition of Subjects

The total number of subjects screened and the reasons for failing screening will be reported.

Subject disposition information will be summarized for all randomized subjects by treatment group and overall. The summaries will include the following information:

- Subjects randomized
- Subjects randomized and Treated with Study Drug
- Subjects completed study treatment
- Subjects early terminated from study treatment (including by reason for early termination of study treatment, and if the reason for early termination of study treatment is related to public health emergency)
- Subjects completed study
- Subjects discontinuing from study (including by reason for discontinuation of study, and if the reason is related to public health emergency)

Data related to disposition (including the date of informed consent signed, the dates of first dose and last dose of study drug, primary reason for subject discontinuation of study treatment, the date of last visit, study completion status) will be listed.

Visit status (performed on time, out of window, missed), type of visit (on site, telephone), the impact of public health emergency to the visit will be summarized and listed.

#### 4.4.2 **Protocol Deviations**

Major analysis protocol deviations that could potentially affect the efficacy conclusions of the study will be identified prior to database lock. Major analysis protocol deviations may include, but are not limited to:

- Randomized subjects who did not satisfy inclusion criteria
- Randomized subjects who did not satisfy exclusion criteria
- Subjects whose randomized and actual treatments differ at any time point
- Subjects who received an excluded concomitant treatment or medication
- Subjects who are not 80-120% compliant with study medication
- Subjects who received rescue medication within 6 hours prior to spirometry testing

Subjects with major analysis protocol deviations will be identified before the database lock and provided in a listing of subjects excluded from per-protocol (PP) efficacy analyses. In addition, a listing of all major deviations will be provided whether they impact the analysis or not. All decisions to exclude subjects from the PP analysis set will be made prior to unblinding in the final blinded data review (BDR) meeting and report.

The PD summaries will include the following information, using Randomized Set:

- the number and percentage of subjects with a major PD by treatment group and overall and by type of deviation
- the number and percentage of subjects with a major PD leading to exclusion from the PP by treatment group and overall, and by type of major deviation leading to exclusion
- the number and percentage of subjects with a major PD related to COVID-19 by treatment group and by type of deviation

#### 4.5 Analysis Sets

The **Screened Set** consists of all subjects who sign the study informed consent. Screen failures are subjects who sign the study informed consent but fail to meet study requirements during screening or prior to randomization.

The **Randomized Set** consists of all subjects that are randomized to a treatment on Day 1. Subjects in this population will be reported according to the treatment they were randomized to, regardless of any dosing error. The Randomized Set will be predominantly used for listings of data.

The **Safety Analysis Set (SS)** is defined as all subjects who receive at least one dose of study drug. Subjects in this population will be summarized according to the actual treatment they received. The treatment received will only be different from the randomized treatment if the subject took the wrong dose or study drug for > 50% of the entire double-blind treatment period. All safety analyses will be performed using the SS.

The **Full Analysis Set (FAS)** consists of all randomized subjects who received at least one dose of study drug and have at least one recorded post-baseline efficacy assessment. Subjects in this set will be analyzed and summarized according to their assigned treatment and strata at randomization. The FAS will be used for all efficacy endpoints.

The **Per-Protocol (PP) Analysis Set** consists of subjects in the FAS who had no major protocol violation that would impact significantly on the primary endpoint. The list of major protocol deviations will be finalized prior to database lock. All decisions to exclude subjects from the PP analysis set will be made prior to unblinding in the final blinded data review (BDR) meeting and report. Data will be summarized and analyzed according to the treatment a subject actually received and strata they actually belong to. The PP analysis set will be used for the primary endpoint only.

Analysis Set information will be summarized for all randomized subjects by treatment group and overall. The table will include rows for the number (%) of subjects randomized, randomized but not treated, Safety Set (SS), Full Analysis Set (FAS), Per-Protocol (PP) Analysis Set.

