**Figure 1-1: Study Diagram**

[figure not shown]

Table 1-1: Study Schedule

VISIT	1 (Screen 1)	2 (Screen 2) 	3 Randomization	4	5	6 (EoT)	Early term (ET)	Follow up (Telephone)
NOMINAL DAY (ALLOWABLE WINDOW)	-14 (-30 to -4)	-7 (-10 to -4)	1	29 (22-36)	57 (50-64)	85 (78-92)		7-14 days after V6/ET
NOMINAL WEEK	-2	-1	0	4	8	12		
Written informed consent	x							
IVRS/IWRS transaction	x		x	x	x	x	x	x
Demography and medical history (incl. COPD, smoking, and exacerbation history)	x							
Review concomitant medications	x	x	x	x	x	x	x	x
Physical examination	x					x	x	
Chest X-ray (if not done in past 12 months)	x							
Height and weight	x							
Vital Signs (supine or semi-recumbent blood pressure, pulse rate)	x		x 			x 	x	
12-lead ECG (supine or semi-recumbent)	x		x 			x 	x	
Spirometry (FEV 1 , FVC) pre-bronchodilator		x						
Spirometry (FEV 1 , FVC) 45 min post-ipratropium (500 mcg nebulized)		x						
Laboratory Safety – Blood and Urinalysis	x					x	x	
Pregnancy Test	x		x	x	x	x	x	
Dispense Rescue Medication (salbutamol pMDI)	x		x	x	x			
Dispense Daily Diary	x		x	x	x			
Record Adverse Events	x	x	x	x	x	x	x	x

VISIT	1 (Screen 1)	2 (Screen 2) 	3 Randomization	4	5	6 (EoT)	Early term (ET)	Follow up (Telephone)
NOMINAL DAY (ALLOWABLE WINDOW)	-14 (-30 to -4)	-7 (-10 to -4)	1	29 (22-36)	57 (50-64)	85 (78-92)		7-14 days after V6/ET
NOMINAL WEEK	-2	-1	0	4	8	12		
Medication Training	x		x					
Pre-dose Spirometry (FEV 1 , FVC), -45 and -15 min pre-dose.			x	x	x	x	x	
Complete BDI/TDI 			x	x	x	x	x	
Complete SGRQ			x			x	x	
Complete mMRC			x					
Randomization			x					
Administer Study Medication in Clinic			x	x	x	x		
Dispense Outpatient Study Medication			x	x	x			
Post-dose Spirometry (FEV 1 , FVC), 5, 15, and 30 minutes, and 1, 1.5, and 2h			x			x		
PK sampling			x	x	x	x		
Record Rescue Medication and Study Drug in Diary, Review at Clinic Visits		x	x	x	x	x	x	

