### 6.2.2 Visit 4 (Day 29 ± 7 days)

Procedures will be completed in the following order:

- Ensure sufficient washout of restricted medications per [Table 5-1](#) prior to spirometry assessments.
- Complete the following questionnaire: TDI.
- Assess and record AEs.
- Review and record concomitant medications.
- Compliance check for study drug via drug returns or daily diary.
- Collect and review rescue medication use recorded in daily diary.
- Urine or serum pregnancy test (if female of child-bearing potential).
- Dispense study drug via IVRS/IWRS.
- Spirometry (FEV1, FVC) at -45 and -15 minutes pre-dose.
- Blood will be collected within 30 minutes pre-dose for PK analysis.
- Administer LABA or ICS/LABA if the subject is taking one of these drugs.
- Study drug dosing via nebulizer. Dosing time will be recorded in date, hours, and minutes corresponding to the start and completion of nebulization. Pre-dose assessment time is defined relative to the start of nebulization. Post-dose assessment time is defined relative to the completion of nebulization. Study drug administration must be performed in a different room from that used for PK blood sampling and processing to avoid contamination of PK samples.
- Blood will be collected at any time between 1 – 30 minutes post-dose for PK analysis. The actual PK sampling time will be recorded in date, hours, and minutes.
- Dispense rescue medication as needed.
- Dispense daily diary.

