### 6.2.3 Visit 5 (Day 57 ± 7 days)

Procedures will be completed in the following order:

- Ensure sufficient washout of restricted medications per [Table 5-1](#) prior to spirometry assessments.
- Complete the following questionnaire: TDI.
- Assess and record AEs.
- Review and record concomitant medications.
- Compliance check for study drug via drug returns or daily diary.
- Collect and review rescue medication use recorded in daily diary.
- Urine or serum pregnancy test (if female of child-bearing potential).
- Dispense study drug via IVRS/IWRS.
- Spirometry (FEV1, FVC) at -45 and -15 minutes pre-dose.
- Blood will be collected within 30 minutes pre-dose for PK analysis.
- Administer LABA or ICS/LABA if the subject is taking one of these drugs.
- Study drug dosing via nebulizer. Dosing time will be recorded in date, hours, and minutes corresponding to the start and completion of nebulization. Pre-dose assessment time is defined relative to the start of nebulization. Post-dose assessment time is defined relative to the completion of nebulization. Study drug administration must be performed in a different room from that used for PK blood sampling and processing to avoid contamination of PK samples.
- Blood will be collected at any time between 1 – 30 minutes post-dose for PK analysis. The actual PK sampling time will be recorded in date, hours, and minutes.
- Dispense rescue medication as needed.
- Dispense daily diary.

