## 7.2 Analysis Set Definitions

### 7.2.1 Safety Analysis Set

The safety analysis set (SS) will include all subjects who received at least one dose of study drug. Data will be summarized according to the treatment a subject actually received.

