## 4.9 Treatment Compliance

Subjects will take nebulized study drug (3mL sealed plastic vial) once daily during the 12-week double-blind placebo-controlled treatment period.

The number of dispensed, used, unused and lost vials will be counted and recorded as part of the drug accountability. The primary assessment of compliance will be based on the vial counts.

Compliance is based on the count of number of study drug vials taken as recorded on the Drug Accountability eCRF page. Treatment compliance in percent will be calculated as:

Compliance (%) = (Number of vials taken / Number of expected vials)  $\times$  100

where Number of expected vials =  $1 \times \text{study drug exposure}$ 

Details of study drug exposure are described in Section 4.11.1.

The compliance will be classified (e.g. <80%, 80%-120\%, >120%). If the compliance is outside of 80%-120%, a subject is considered non-compliant. The number and percentage of subjects in the above categories will be summarized based on Safety Set by treatment group and overall.

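### The safety set's 50% rule is set against the 12-week treatment period, so, read literally, a subject who took only the other treatment and stopped early is reported under a treatment never taken

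*SAP*

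**What the plan says.** For the safety set, Protocol 7.2.1 states: "Data will be summarized according to the treatment a subject actually received". It gives no threshold and does not say how mixed exposure is to be classified.

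SAP 4.5 starts from the same principle, "Subjects in this population will be summarized according to the actual treatment they received", and its next sentence restricts it: "The treatment received will only be different from the randomized treatment if the subject took the wrong dose or study drug for > 50" per cent of the period. The condition in full is having taken "the wrong dose or study drug for > 50% of the entire double-blind treatment period". All safety analyses use this set.

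SAP 4.5 does not define the denominator. SAP 4.9 describes dosing as "once daily during the 12-week double-blind placebo-controlled treatment period". SAP 4.11.1 defines each subject's own exposure, from first to last dose date, but SAP 4.5 does not refer to it.

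SAP 4.13, which sets out clarifications to the protocol's wording, does not mention the 50% rule.

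**The concern.** An as-treated safety set exists so that events are counted under the drug that could have caused them. A majority rule is a reasonable way to classify a subject who took both treatments. It should never change the classification of a subject who took only one. With a fixed 12-week denominator it can, because an early stop caps the share of the period that any treatment can reach.

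The cap is also linked to safety. Protocol 4.2.4 ends study drug after a moderate or severe exacerbation, and exacerbations are themselves a safety endpoint (Protocol 3.2.2.2). The event that most needs correct attribution can therefore be the one that keeps the subject below the threshold.

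**Working it through.** The plan gives no computed figure on this point to reproduce. The check applies the stated threshold to the stated schedule.

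**Inputs**
- Threshold: more than 50% (SAP 4.5).
- Period: 12 weeks once daily (SAP 4.9), so 12 × 7 = 84 days, or 85 if the Day 85 clinic dose is counted.
- Supply: the row "Dispense Outpatient Study Medication" in Protocol Table 1-1 is marked at Visits 3, 4 and 5, giving three intervals of nominally 28 days.
- Visit windows: Visit 4 on Days 22–36, Visit 5 on Days 50–64, Visit 6 on Days 78–92 (Protocol Table 1-1).
- Assumption: the clinic dose at a visit comes from the newly dispensed supply.

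**Step 1. Subject takes only the other treatment, then stops**

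Share = doses of the other treatment ÷ denominator.

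| Doses taken | Share of 84 days | Moved? | Share of own dosing days | Moved? |
|---|---|---|---|---|
| 7 | 7/84 = 8% | no | 100% | yes |
| 28 | 28/84 = 33% | no | 100% | yes |
| 35 | 35/84 = 42% | no | 100% | yes |
| 42 | 42/84 = 50.0% | no | 100% | yes |
| 43 | 43/84 = 51.2% | yes | 100% | yes |

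With 85 days the cut falls in the same place: 42/85 = 49.4% and 43/85 = 50.6%.

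**Step 2. How many errors are needed**

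A wrong Day 1 supply lasts until the day before Visit 4. That is nominally 28 doses, and 21 to 35 across the window (22 − 1 = 21; 36 − 1 = 35). So one dispensing error followed by a stop before Visit 4 gives at most 35/84 = 42%, always below the threshold. Taking only the other treatment for 36 to 42 doses would need a second wrong supply or a late Visit 4.

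**Step 3. One wrong supply in a subject who completes**

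Nominally 28/84 = 33%, or 28/85 = 33% of own days. Both rules leave the subject in the randomised arm.

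Each window allows 15 days, so there are 15 × 15 × 15 × 3 = 10,125 visit-day and interval combinations. Measured against the subject's own time to Visit 6, one supply passes 50% in 20 of them. All 20 are the Visit 4 to Visit 5 interval, with a maximum of 42/78 = 54%. Against a fixed 84 days that interval reaches exactly 42/84 = 50%, and the Visit 5 to Visit 6 interval can just pass it (43/84 = 51%).

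**Step 4. Size**

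The documents give no rate of dispensing errors. Assuming one to three misplaced subjects, each with a given event, the incidence in a planned arm of 160 shifts by 1/160 = 0.6, 2/160 = 1.25 or 3/160 = 1.9 percentage points. The between-arm difference shifts by about twice that.

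**The case against.** **The denominator is open to another reading.** SAP 4.11.1 measures exposure over the treatment period from first to last dose. On that basis a subject who took only the wrong drug is at 100% and is always moved. This stands as far as it goes: the text does not settle the matter, so misclassification follows from the literal wording and not from every reading. The literal wording is still the more natural one, given that SAP 4.5 refers to the whole period and SAP 4.9 calls it 12 weeks.

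**A reader might infer that any one-visit dispensing error puts the subject in the wrong arm.** The documents do not support this. A completer with one wrong supply took the randomised drug on about two thirds of days, and any majority rule leaves that subject where SAP 4.5 does. What is missing there is only a display of events by drug at onset.

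**A reader might infer that the rule always makes revefenacin look safer.** This is not shown. Mixing arms dilutes differences in either direction. It would hide an excess of antimuscarinic events, but it would also hide a reduction in exacerbations if there is one.

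**Affected subjects can be traced.** SAP 4.4.2 names a mismatch at any time point as a possible major deviation, and all major deviations are listed. Adverse events and exposure are listed too (SAP 4.11.1 and 4.11.2). This is true, but no planned output moves such a subject in the tables or shows the drug being taken at onset.

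**The SAP may modify the protocol.** Protocol section 7 allows this outside major changes to the primary endpoint. That makes the rule permissible. It does not remove the conflict between two adjacent sentences of SAP 4.5.

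**Conclusion.** The point holds as a minor correction. On the literal 12-week denominator, a subject who took only the other treatment and stopped after 42 or fewer doses is summarised under a treatment never taken, contrary to Protocol 7.2.1. One wrong Day 1 supply and a stop before Visit 4 is sufficient.

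This rests on reading the period as the planned 12 weeks, which the SAP supports but does not state in SAP 4.5. Few subjects are expected, since supply is controlled by IVRS/IWRS (Protocol 5.5). Safety summaries are descriptive with no treatment comparison (SAP 4.11). Efficacy in the full analysis set uses the assigned treatment, so the primary result and the sample size do not change.

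**What to change.** In SAP 4.5, replace the reference to the whole double-blind period with *the subject's own dosing days, from first to last dose (SAP 4.11.1)*. Count days on which a dose was taken, so that missed doses do not recreate the problem. Anyone who took only one treatment is then always reported under it.

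Keep the majority rule for subjects who took both treatments. For them, add a flag or a short listing of adverse events showing the drug being taken at onset, or the last one taken if the event starts after the final dose. A listing is preferable to a table by drug at onset, which would put one subject in two arms with no defined denominator.

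Record the rule in SAP 4.13 as a clarification of Protocol 7.2.1.

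Cost: one sentence, one entry in SAP 4.13, and one flag or listing for a handful of subjects. SAP 4.4.2 already expects treatment mismatches to be identified, so no new data are needed.

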## 4.6 Demographic and Other Baseline Characteristics

## 4.6.1 Demographics

Baseline demographics are collected at the Screening Visit 1. Descriptive statistics will be prepared for the demographics by treatment group and overall using the Full Analysis Set (FAS) population. If the Per-Protocol (PP) Analysis Set is different to FAS, a separate demographics table will be included for this population as well. If the Randomized Set is different to FAS, demographics will also be reported for Randomized Set. The following information will be included in the summary:

- Age in years
- Age group (<65 years,  $\geq$ 65 years)
- Sex (Male, Female)
- Race (Asian Chinese, Asian Not Chinese)
- Height
- Weight
- Body mass index  $(kg/m^2)$

Demographic data will be listed using the Randomized Set.

## 4.6.2 Baseline Smoking, Alcohol and Drug History

Baseline smoking, alcohol and drug history is collected at Screening Visit 1 and will be summarized by treatment group and overall (FAS population). The endpoints will include:

- Smoking status (Current, Former)
- The number of years smoked (derived)
- The number of pack-years smoked (as collected)
- Subject with history of alcohol abuse within the past 5 years (Yes, No)
- Subject with history of illegal or recreational drug within the past 5 years (Yes, No)

Smoking, alcohol and drug history will be listed using the Randomized Set.

#### 4.6.3 **Baseline Spirometry**

Baseline spirometry data will be summarized by treatment group and overall (FAS population). Data will be collected at Screening Visit 2 for the following endpoints:

- pre- and post-bronchodilator FEV1(L);
- reversibility to ipratropium (Yes, No as collected);
- predicted normal FEV1 (L) and percent predicted FEV1 (%)
- pre- and post-bronchodilator FVC (L);
- pre- and post-bronchodilator FEV1/FVC ratios.

All baseline spirometry data will be listed using the Randomized set. If the Randomized Set is different to FAS, demographics will also be reported for the FAS.

Data for baseline  $FEV_1$  and FVC assessments used in the derivation of the primary and secondary endpoints will be collected at -45 and -15 minutes prior to dosing of study medication on Day 1 (Randomization Visit 3).

Baseline is defined as the average of the -45 and -15 minute measurements. If either of the two pre-dose measures is missing, the baseline will be set to the value of the remaining non-missing measure. If both pre-dose values are missing then the baseline will be set to missing.

This baseline spirometry data will be presented in tables with the primary and secondary spirometry endpoints.

#### 4.6.4 Baseline COPD Disease-Related Characteristics

Data on COPD disease-related characteristics will be summarized (FAS population) by treatment group and overall. Presentations will include:

- COPD Duration in years (derived);
- Number of COPD Exacerbations in past 12 months;
- Number of COPD Exacerbations requiring hospitalization in previous 12 months
- Concomitant ICS use (Yes, No as collected);
- Concomitant LABA use (Yes, No as collected);
- Concomitant ICS/LABA use (Yes, No), derived from Concomitant ICS use and Concomitant LABA use;
- GOLD Airflow Categories 1-4 (derived);
- GOLD Categories A-D (as collected).

COPD Disease-Related Characteristics will be listed using the Randomized Set.

